10.6 Procedures for Reporting Serious Adverse Events

All SAEs occurring during the course of the study, as defined by the protocol, regardless of the relationship to the study drug, must be reviewed and reported by the Investigator to the Sponsor through the contract research organization (CRO), AMIT, [name], within 24 h from the point in time when the Investigator becomes aware of the SAE.

The information collected by the Investigator will include at minimum the following: patient number, the criteria met for the AE being serious, the event term, date and time of onset, a narrative description of the event, and an assessment by the Investigator as to the severity of the event and relatedness to the study drug.

V4.0_8 Jul 2024 Page 58 of 68

The Investigator is obligated to assess the relationship between study intervention and each AE/SAE. A "reasonable possibility" of a relationship conveys that there are facts, evidence, and/or arguments to suggest a causal relationship, rather than that a relationship cannot be ruled out. The Investigator will use clinical judgment to determine the relationship. Alternative causes, such as underlying disease(s), concomitant therapy, and other risk factors, as well as the temporal relationship of the event to study intervention administration, will be considered and investigated. The Investigator will also consult the BSI-045B Investigator's Brochure, or for marketed products, the product information, in making their assessment.

If the Investigator does not know whether or not the study intervention caused the event, then the event will be handled as "related to study intervention" for reporting purposes, as defined by the Sponsor in the protocol. In addition, if the Investigator determines that an SAE is associated with study procedures, the Investigator must record this causal relationship in the source documents and CRF, and report such an assessment in the dedicated section of the SAE Report Form and in accordance with the SAE reporting requirements.

The Investigator will complete the SAE Report Form with their signature and date on each page of the report, scan it into a PDF file, and send the file to AMIT and the Sponsor through e-mail [contact] and submit to the local approving IRB within 24 hours of first awareness of this SAE. In case the Investigator has no access to e-mail, the signed SAE Report can be sent to AMIT via fax at the number [name] and be additionally shared with the Sponsor by AMIT.

The SAE Report will be further processed by AMIT into the pharmacovigilance database and submitted to FDA in case of serious, unexpected, and related AEs (suspected unexpected serious adverse reaction [SUSAR]) within 7 days of the day of first awareness for lifethreatening or more severe cases, or 15 days of the day of first awareness for the cases at all other severity levels. The reports submitted to FDA will be forwarded to the study operation service CRO (ICON Clinical Research Limited [ICON]) through e-mail in the format of XML or MedWatch 2500A Form for the purpose of sharing with all the Investigators at the earliest availability. The information from all the SAEs will be forwarded to ICON periodically.

The Sponsor will promptly notify the Investigator about important safety or toxicology information as it becomes available. It is the responsibility of the Investigator to promptly notify the IRB about new and relevant safety information regarding the IP, including serious adverse drug reactions involving risk to human patients, in accordance with the applicable policies. The SAE reporting period is the same as the AE reporting period (starts with the signing of the ICF and continues through the termination visit).

The Sponsor will notify the FDA or all serious, unexpected, and related AEs within 15 calendar days after the study team receives knowledge of the event, and all life-threatening and/or fatal events within 7 calendar days after the study team receives knowledge of the event.

V4.0_8 Jul 2024 Page 59 of 68

10.7 Follow-up of SAEs and AEs

The Investigator is obligated to perform or arrange for the conduct of supplemental measurements and/or evaluations as medically indicated or as requested by the Sponsor to elucidate the nature and/or causality of the AE or SAE as fully as possible. This may include additional laboratory tests or investigations, histopathological examinations, or consultation with other healthcare providers. If a subject dies during participation in the study or during a recognized follow-up period, the Investigator will provide AMIT with a copy of any postmortem findings including histopathology. New or updated information will be recorded in the originally completed CRF. The Investigator will submit any updated SAE data to the Sponsor, AMIT and IRB within 24 hours of receipt of the information. AMIT will further process the SAE in the same time frame as for the initial SAE Report.

10.8 Special Situations

Regardless of whether associated with an AE or SAE, special situation reports should be generated for all instances of medication error, abuse, misuse or overdose, occupational exposure, drug interactions, exposure via breastfeeding, unexpected benefit, transmission of infectious agents via the study drugs, product complaints, counterfeit of falsified medicine, and pregnancy, and forwarded to Sponsor through AMIT via e-mail or fax within one (1) working day.

10.9 Pregnancy Reporting

If a female study patient becomes pregnant during the study or within 90 days since the last dose, BSI-045B should be discontinued and the Sponsor notified within one working day using a Pregnancy Monitoring Form.

If the partner of a male patient becomes pregnant within 90 days since the last dose the Sponsor should be notified as soon as possible. Consent by the female partner of a male patient must be obtained prior to any data collection.

Pregnant patients or pregnant partners of male patients should be advised to inform their treating physician of their involvement in study BSI-045B-002.

All pregnancies must be followed up through delivery or other fetal outcome. An abnormal pregnancy outcome (eg, spontaneous abortion, fetal death, stillbirth, congenital anomalies, ectopic pregnancy) is considered an SAE, reportable to the Sponsor within one working day.

V4.0_8 Jul 2024 Page 60 of 68

11 STATISTICAL METHODS

11.1 Sample Size

With a minimum sample size of 20 patients, the maximum one-sided 95% confidence interval width for the proportion achieving EASI75 equals 21%.

With a maximum sample size of 24 patients, the maximum one-sided 95% confidence interval width for the proportion achieving EASI75 equals 19%.

11.2 Statistical Approach

Statistical analyses will be descriptive in nature, with frequencies and percentages generated for categorical variables and mean, standard deviation, median, minimum, and maximum values generated for continuous variables. Exact one-sided 95% confidence intervals will be generated for primary and select secondary efficacy endpoints based on proportions.

Additional details regarding the statistical analyses will be presented in the Statistical Analysis Plan.

11.3 Study Population

11.3.1 Patient Disposition

The number of patients screened, enrolled, and dosed from screening to the completion of the study will be listed, and the number and percentage of patients who have completed or withdrawn from the study by dose group will be presented.

Patients who discontinue treatment will be summarized and the primary reason for discontinuation. Patient disposition will be summarized.

11.3.2 Protocol Deviations

A protocol deviation is defined as any change, divergence, or departure from the study design or procedures defined in the protocol.

An important protocol deviation is defined as a protocol deviation that might significantly affect the completeness, accuracy, and/or reliability of the study data or that might significantly affect a patient's rights, safety, or well-being. Important protocol deviations may result in the removal of patients from the study and the analysis.

Protocol deviations will be classified as important and non-important by the Sponsor and Investigators prior to database lock.

Protocol deviations will be summarized.

V4.0_8 Jul 2024 Page 61 of 68

11.3.3 Baseline Characteristics

Baseline characteristics will be summarized descriptively, for demographic information, prior medical history, physical examination, vital signs, 12-lead ECG, and clinical laboratory tests. Baseline is defined as the most recent non-missing measurement prior to the patient receiving their first dose of study drug.

11.4 Efficacy Assessments

Statistical analysis of efficacy assessments includes changes in the EASI, IGA, and PP-NRS. Methods are described in detail in the SAP.

11.5 Safety Assessments

All AEs will be coded using the Medical Dictionary for Regulatory Activities. An AE (classified by preferred term) will be considered a TEAE if it was not present before the first dose of study drug or if it was present before the first dose of study drug but increased in severity during the assessment period for AEs. The incidence of TEAEs will be summarized by system organ class and preferred term. Multiple AEs mapped to the same preferred term will be counted once per patient.

Concomitant medications will be coded using The World Health Organization (WHO) Drug Dictionary with generic term and Anatomical Therapeutic Chemical (ATC) code and summarized by ATC code and WHODrug generic name. Safety laboratory findings, AEs, vital signs, and 12-lead ECGs will be summarized using descriptive statistics. Values and changes from baseline at scheduled time points will be summarized. Laboratory data will be listed and values and changes from baseline will be summarized.

11.6 Pharmacokinetic Data Analysis

Pharmacokinetics listings will be provided. Pharmacokinetic parameters will be estimated using NONMEM® Version 7.4 (or later versions) software with compartmental modeling analysis. Based on data availability, a PK/PD model will be developed to evaluate the relationships between serum BSI-045B and clinical efficacy.

11.6.1 Analysis of Serum Drug Concentration versus Time Data

The mean (and standard deviation) serum BSI-045B concentration-time profile in a semi-logarithmic scale for all patients will be plotted based on planned sampling time points. Individual concentration-time profiles in a semi-logarithmic scale for each patient will be plotted based on actual blood collection times.

11.7 Immunogenicity Analysis

The titers of ADA-positive patients will be listed, and the number, incidence, and 95% CI of patients with treatment emergent ADA after administration of BSI-045B will be described by

V4.0_8 Jul 2024 Page 62 of 68

blood sampling time points. The time to onset, titer, and duration of the presence of ADAs will be described using the mean, SD, median, quartiles, minimum, and maximum.

11.8 Pharmacodynamic Biomarker Analysis

The biomarker levels of patients (values and percent changes from baseline) will be summarized by descriptive statistics.

V4.0_8 Jul 2024 Page 63 of 68

12 INVESTIGATOR AND ADMINISTRATIVE REQUIREMENTS

12.1 Institutional Review Board

The protocol and ICF for this study must be reviewed and approved by an appropriate IRB before patients are enrolled in the study. It is the responsibility of the Investigator to assure that the study is conducted in accordance with current country and Local Regulations, International Council for Harmonisation of Technical Requirements for Pharmaceuticals for Human Use, GCP, and the Declaration of Helsinki. A letter, documenting the approval that specifically identifies the protocol by number and title as well as the Investigator, must be received by the Sponsor before initiation of the study. Amendments to the protocol will be subject to the same requirements as the original protocol.

Upon the completion or termination of the study, the Investigator will notify the IRB.

12.2 Informed Consent

To obtain valid consent, each patient must be provided with written information describing the nature and duration of the study, the risks associated with the study, the burden on the patient and details of what will happen to any personal or health information collected. The patient must be provided with this information, given an opportunity to ask questions, and be given time to be able to consult with support persons or physicians such as a general practitioner. The patient must sign a written ICF indicating that they have read and understood the information sheet and what they are being asked to do. The ICF must be in a language in which the patient is fluent and must be signed before study-specific procedures are conducted. The signed and dated ICF will be retained with the study records.

12.3 Data Reporting and Case Report Forms

Data for each patient will be entered into the CRF and verified by the Investigator. It is the Investigator's responsibility to ensure the accuracy, completeness, legibility, and timeliness of the data reported on the patient's CRF. Source documentation supporting the CRF data should indicate the patient's participation in the study and should document the dates and details of study procedures, AEs, and patient's clinical status.

The Investigator or designated representative should complete the CRF as soon as possible after information is collected, preferably on the same day that a study patient is seen for an examination, treatment, or any other study procedure. Any outstanding entries must be completed immediately after the final examination. CRF data will be processed in a US 21 Code of Federal Regulations Part 11-compliant system.

12.4 Retention of Data

Regulations require that a copy of records (eg, laboratory data slips, source documents, test article disbursement records) that support case records of this study must be retained in the files of the responsible Investigator for a minimum of 15 years.

V4.0_8 Jul 2024 Page 64 of 68

12.5 Deviations from the Protocol

The Investigator will not deviate from the protocol. In medical emergencies, the Investigator will use medical judgment and will remove the patient from immediate hazard, and then notify the Sponsor's Medical Monitor and the IRB promptly regarding the type of emergency and course of action taken. Any action in this regard will be recorded on the appropriate CRF. Any other changes or deviations in the protocol will be made as an amendment to the protocol and must be approved by the Sponsor and the IRB before the changes or deviations are implemented. The Sponsor will not assume any responsibility or liability for any deviation or change that is not described as part of an amendment to the protocol, or protocol clarification letters.

12.6 Study Monitoring

The Investigator will allow representatives of the Sponsor to periodically audit (at mutually convenient times before, during, and after the study has been completed) all CRFs and relevant portions of office, clinical, and laboratory records for each patient. Appropriate source documents, including documents that support patients' eligibility (eg, medical history, concomitant medications) should be made available to the Clinical Monitor. The monitoring visits provide the Sponsor with the opportunity to evaluate the progress of the study; verify the accuracy and completeness of CRFs; assure that all protocol requirements, applicable regulations, and Investigator's obligations are being fulfilled; and resolve any inconsistencies in the study records.

12.7 Disclosure of Data

Individual patient medical information obtained as a result of this study is considered confidential and disclosure to third parties other than those approved by the Sponsor is prohibited. Patient confidentiality will be further assured by utilizing patient identification code numbers to correspond to treatment data in the computer files. The study personnel, employees of the regulatory agencies, including FDA and the Sponsor and its agents will need to review patient medical records in order to accurately record information for this study. If results of this study are reported in medical journals or at meetings, the patients' identities will remain confidential.

V4.0_8 Jul 2024 Page 65 of 68

# Protocol No.: BSI-045B-002

Version: V1.0

# **Version History**

Version	Date	Description of Changes
1.0	September 13, 2024	Original Document.

Statistical Analysis Plan Version Date: September 13, 2024

Protocol No.: BSI-045B-002 Version: V1.0

# **Abbreviations**

AD	Atopic Dermatitis	
ADA	Antidrug Antibody	
AE	Adverse Events	
ATC	Anatomic Therapeutic Chemical Classification	
AUC	Area Under the Serum Drug Concentration-time Curve	
BMI	Body Mass Index	
CI	Confident Interval	
CRF	Case Report Form	
CS	Clinically Significant	
CS CSR		
	Clinical Study Report	
CTCAE	Common Terminology Criteria for Adverse Events	
EASI	Eczema Area and Severity Index	
ECG	Electrocardiography	
eCRF	Electronic Case Report Form	
EDC	Electronic Data Capture	
ICH	International Conference of Harmonization	
IGA	Investigator's Global Assessment	
LOCF	Last Observation Carried Forward	
MedDRA	Medical Dictionary for Regulatory Activities	
PD	Pharmacodynamic	
PK	Pharmacokinetics	
PP-NRS	Peak Pruritus Numerical Rating Scale	
PT	Preferred Term	
Q2W	Every 2 Weeks	
QW	Every Week	
SAE	Serious Adverse Event	
SAP	Statistical Analysis Plan	
SC	Subcutaneous	
SOC	System Organ Class	
TEAE	Treatment-Emergent Adverse Event	
WHODrug	World Health Organization Drug Dictionaries	
I	ı	

#### 1. Introduction

The following Statistical Analysis Plan (SAP) provides the outline for the statistical analysis of the data from the BSI-045B-002 study.

The planned analyses identified in this SAP may be included in clinical study reports (CSRs), regulatory submissions, or future manuscripts. In addition, post hoc exploratory analyses not necessarily identified in this SAP may be performed to further examine study data.

# 2. Project Overview

#### 2.1 Study Design

The study design is presented in the Schema. The study is a multicenter clinical trial and is designed as a proof-of-concept study to evaluate the efficacy, safety, tolerability, PK, immunogenicity, and PD of BSI-045B following SC injections.

The present study, which is intended to assess the efficacy and safety of BSI-045B in moderate to severe AD patients, is being conducted as a proof-of-concept study prior to performing a more traditional Phase 2 trial. If this study is successful, the Sponsor plans to conduct a future Phase 2b, randomized, blinded, dose-finding trial that will formally compare BSI-045B with placebo and/or other treatments for AD.

The study will enroll patients with moderate to severe AD. Eligible patients will receive BSI-045B 300 mg treatment, firstly at every week (QW) during Week 1 to Week 4, and then every 2 weeks (Q2W) to Week 24.

Patients will start with a washout period for anti-AD treatment prior to study treatment, including systemic and topical agents and phototherapy. The duration of the washout period varies by therapy and the Investigator should consult section 7.2 in the protocol. Eligible patients who complete the washout period for previous therapies for AD will be treated with BSI-045B as described above.

#### **Monitoring by Safety Steering Committee (SSC)**

The SSC will monitor the study and will be composed of representatives from the Sponsor, the National Principal Investigator, and independent physicians, as indicated in the SSC charter. The SSC will formally assess safety findings when 20 patients complete dosing at Week 12. The SSC will assess all events, especially treatment-related SAEs that might prompt a change to the study.

#### **Assessment of Primary Efficacy Endpoint**

The primary efficacy endpoint is the proportion of patients with ≥EASI75 at Week 26 (2 weeks after last dose at Week 24).

#### Follow-up Period

After the Treatment Period, there will be a 12 -week Follow-up Period.

Protocol No.: BSI-045B-002 Version: V1.0

#### SCHEMA: BSI-045B-002 Study Design

# 2.2 Study Objectives & Endpoints

Objectives and endpoints for this study are detailed in Table 1.

Table 1: Objectives and Endpoints in BSI-045B-002 Study

Objectives	Endpoints			
Primary				
Primary Efficacy Objective:	Primary Efficacy Endpoint:			
To evaluate the efficacy of BSI-045B in patients with moderate to severe atopic dermatitis (AD)	Proportion of patients with ≥Eczema Area and Severity Index (EASI)75 at Week 26 (2 weeks after last dose at Week 24)			
Primary Safety Objective:	Primary Safety Endpoint:			
To evaluate the safety and tolerability of BSI-045B in patients with moderate to severe AD	Safety and tolerability as evidenced by the incidence of adverse events (AEs), anti-BSI-045B antidrug antibody (ADA) formation, clinical laboratory evaluations, 12-lead electrocardiography (ECGs), vital signs, and physical examinations. The relationships between study drugs and AEs will be evaluated by the Investigators.			
Secondary				
To evaluate the pharmacokinetics (PK) of BSI-045B	Pharmacokinetics listings will be provided. PK parameters might be estimated through compartmental modeling. Additionally, the PK/Efficacy relationship might be explored.			
To evaluate the immunogenicity of BSI-045B	Anti-BSI-045B ADA during and post BSI-045B treatment			
Exploratory				
To assess additional efficacy and safety outcomes of BSI-045B	
 
Proportion of patients with EASI90 at Week 26 (2 weeks after last dose at Week 24)
 
Proportion of patients with EASI50 at Week 26 (2 weeks after last dose at Week 24)
 
Percent change from baseline in EASI at each visit
 
Proportion of patients achieving Investigator's Global Assessment (IGA) 0 or 1 at 26 (2 weeks after last dose at Week
 
			

	24)	
	Percent changes in PP-NRS scores at Week	
	26 (2 weeks after last dose at Week 24)	
	Proportion of patients achieving Facial IGA	
	0/1 at Week 26 (2 weeks after last dose at	
	Week 24)	
	Occurrence of conjunctivitis	
To evaluate the PD biomarkers of	Serum levels of thymus and activation regulated	
BSI-045B	chemokine/C-C chemokine ligand 17	
	(TARC/CCL-17), periostin, and IgE during and	
	post BSI-045B treatment	

AD = atopic dermatitis; ADA = antidrug antibody; AE = adverse event; CCL-17 = C-C chemokine ligand 17; EASI = Eczema Area and Severity Index; ECG = electrocardiography; IGA = Investigator's Global Assessment; IgE = immunoglobulin E; PD = pharmacodynamic; PK = pharmacokinetic; PP-NRS = Peak Pruritus Numerical Rating Scale; TARC = thymus and activation regulated chemokine

# 2.3 Sample Size

With a minimum sample size of 20 patients, the maximum one-sided 95% confidence interval width for the proportion achieving EASI75 equals 21%.

With a maximum sample size of 24 patients, the maximum one-sided 95% confidence interval width for the proportion achieving EASI75 equals 19%.

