The SSC will formally assess safety findings when 20 patients complete dosing at Week 12. The SSC will assess all events, especially treatment-related SAEs that might prompt a change to the study.

Assessment of Primary Efficacy Endpoint

The primary efficacy endpoint is the proportion of patients with ≥EASI75 at Week 26 (2 weeks after last dose at Week 24).

Follow-up Period

After the Treatment Period, there will be a 12 -week Follow-up Period.

Methodology

This study is a Phase 2a, proof-of-concept clinical study designed to evaluate the efficacy, safety, tolerability, PK, immunogenicity, and PD of BSI-045B injection, in patients with moderate to severe AD. The study will be unblinded.

BSI-045B treatment will be initiated with a loading dose of 300 mg SC QW for 4 weeks. After that, patients will be treated Q2W to Week 24. After treatment, there will be a 12-week Follow-up Period.

The preferred SC injection site is the abdomen. The thigh can be used as an alternative site for SC injections. A 2.5-mL injection of 120 mg/mL (300 mg total dose) will be administered at a single injection site. After injections, all patients should be monitored at the study sites for at least 30 mins to observe body reactions, including injection site reactions. Any injection site reactions observed after each site visit should be reported to the Investigators by the patients.

The total number of evaluable patients with AD of the study is approximately 20 to 24, patients who do not complete the first 5 doses will be replaced.

The SSC will monitor the study to identify questions concerning safety.

The primary efficacy endpoint is the proportion of patients with ≥EASI75 at Week 26 (2 weeks after last dose at Week 24), compared with baseline (Day 1). Additional efficacy outcomes also include other scores on EASI, Investigator's Global Assessment (IGA), Facial IGA, and Peak Pruritus Numerical Rating Scale (PP-NRS). Efficacy assessments will be conducted at Screening, within the first hour prior to dosing on Day 1, at all subsequent visits, and at the time of early withdrawal from the study.

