AD = atopic dermatitis; AE = adverse event; ALT = alanine aminotransferase; aPTT = activated partial thromboplastin time; AST = aspartate aminotransferase; CCL-17 = C-C chemokine ligand 17; D = day; EASI = Eczema and Severity Index; ECG = electrocardiography; GGT = gamma glutamyl transferase; HbsAg = hepatitis B surface antigen; HBV = hepatitis B virus; HCV = hepatitis C virus; HIV = human immunodeficiency virus; ICF = Informed Consent Form; IGA = Investigator's Global Assessment; IgE = immunoglobulin E; IL = interleukin; INR = international normalized ratio; LDH = lactate dehydrogenase; PD = pharmacodynamic; PH-2 = Patient Health Questionnaire-2; PK = pharmacokinetic; PP-NRS = Peak Pruritus Numerical Rating Scale; PT = prothrombin time; Q2W = every 2 weeks; QW = every week; RBC = red blood cell; SC = subcutaneous; TARC = thymus and activation regulated chemokine; W = week; WBC = white blood cell.

- 1. Screening duration varies by prior AD treatment and the Investigator should consult Section 7.2 for required washout duration. For patients not requiring washout, screening assessments should be conducted after ICF been signed and the screening period will take up to 2 weeks; once they complete their screening assessments and meet all study inclusions/exclusions, the patients will advance directly to W1D1. For patients requiring washout, screening assessments should be conducted after ICF been signed, if all inclusion/exclusions are met, they will be notified by the study sites to start the washout for prior AD treatment. Screening assessments should be repeated if they are performed ≥14 days before W1D1.
- 2. W1D1 pre-dosing is set to confirm the eligibility of patients.
- 3. BSI-045B administration after W4 (4 loading doses) at Q2W interval to Week 24.

V4.0_8 Jul 2024 Page 18 of 68

- 4. Order of assessments: When collecting PK, immunogenicity, biomarker, and clinical laboratory samples, vital signs, and/or ECG assessments are scheduled to occur at the same time point, ECG and vital signs testing will be performed prior to blood collections. The preferred order of assessments is: 1) ECG, 2) vital signs, 3) PK, immunogenicity, and biomarker sampling, 4) clinical laboratory sampling.
- 5. Height and weight, and BSA affected by AD should be determined at the Screening physical examination. BSA affected by AD should also be determined at W1D1 pre-dosing. Symptom-driven examinations will be performed at other time points beyond screening.

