7.3 Replacement of Patients who Withdraw from Treatment

Patients who do not complete the first 5 doses of BSI-045B will be replaced.

V4.0_8 Jul 2024 Page 40 of 68

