#### 4.7.1 Eczema Area and Severity Index (EASI)

The EASI score is a composite index that measures the severity of AD based on the average intensity of four clinical signs (erythema, edema/papulation, excoriations, and lichenification) at four body areas (head, neck, upper extremities, and trunk and lower extremities), and the percentage of affected area for each of the four body areas.

The baseline for EASI is defined as the score measured prior to dosing on Day 1.

Measured values, changes from baseline and percent change from baseline in EASI score will be summarized descriptively on scheduled visit.

The primary efficacy endpoint is the proportion of subjects with EASI75 (a 75% reduction in the EASI score) at 2 weeks after last dose at Week 24. The exploratory endpoints include the proportion of subjects achieving EASI90 at Weeks 26 (2 weeks after last dose at Week 24), the proportion of patients with EASI50 at Week 26 (2 weeks after last dose at Week 24). The corresponding 95% two-sided confidence intervals (CIs) will be calculated using the exact binomial distribution and presented for EASI75, EASI90, and EASI50.

For primary analysis, the percent change from baseline in EASI score, EASI50, EASI75, EASI90 in the EASI score will be calculated with observed data. If the subject has missing value for EASI at scheduled visit, the subject will be excluded from the calculation of proportion at specify visit.

Mean (±standard deviation) of the percent change from baseline in EASI score with observed data will be plotted at scheduled visit.

For sensitivity analysis, the missing value will also be imputed with last observation carried forward (LOCF) method. The imputed data for the percent change from baseline in EASI score will be summarized descriptively on scheduled visit. The proportion of subjects with EASI50, EASI75 and EASI90 at 2 weeks after last dose at Week 26 will also be calculated with imputed data.

A listing of all EASI score will be provided by subject number.

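### The 21% and 19% widths are right for 20 and 24 patients scored at Week 26, but replacement stops at dose 5, so the plan does not secure 20 scored patients

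*SAP*

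**What the plan says.** SAP 2.3, Protocol 11.1 and the Protocol synopsis give the same two statements and no other justification of size: "With a minimum sample size of 20 patients, the maximum one-sided 95% confidence interval width for the proportion achieving EASI75 equals 21" (percent), and "With a maximum sample size of 24 patients, the maximum one-sided 95% confidence interval width for the proportion achieving EASI75 equals 19" (percent).

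The number of evaluable patients appears in the Protocol synopsis in one sentence with the replacement rule: "approximately 20 to 24, patients who do not complete the first 5 doses will be replaced". Protocol 7.3 repeats the rule alone: "Patients who do not complete the first 5 doses of BSI-045B will be replaced". Neither document defines evaluable, and SAP section 3 has no analysis set of that name.

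The primary endpoint is EASI75 at Week 26. SAP 4.7.1 makes this an observed-case analysis: "If the subject has missing value for EASI at scheduled visit, the subject will be excluded from the calculation of proportion at specify visit". LOCF is planned as a sensitivity analysis only.

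The two documents differ on the interval. Protocol 11.2 says "Exact one-sided 95% confidence intervals will be generated for primary and select secondary efficacy endpoints based on proportions", while SAP 4.7.1 says of EASI75, EASI90 and EASI50 that "The corresponding 95% two-sided confidence intervals (CIs) will be calculated using the exact binomial distribution".

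**The concern.** The number that is topped up and the number that is analysed are fixed at different times. A patient who completes dose 5 and later has no Week 26 EASI is not replaced and is not in the denominator of the primary proportion. The precision statement treats 20 as the smallest n for that proportion, yet no rule in the plan keeps it there.

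Precision is the only sample-size argument in either document. A reader planning the Phase 2b study would take 21% as the worst case for the gap between the estimate and its confidence limit. With missing Week 26 scores the gap can be larger.

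**Working it through.** **1. Reproduce the stated figures.** The exact one-sided 95% lower limit for x responders out of n is L = the 5th percentile of Beta(x, n − x + 1). The width is x/n − L, maximised over x.

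- n = 20: the maximum is at x = 13, 0.6500 − 0.4420 = 20.80%, which rounds to the stated 21%.
- n = 24: the maximum is at x = 16, 0.6667 − 0.4786 = 18.81%, which rounds to the stated 19%.

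So 20 and 24 in these statements are numbers of patients scored, with nothing allowed for loss.

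**2. When replacement ends.** The footnote to Protocol Table 1 gives the schedule: "BSI-045B administration after W4 (4 loading doses) at Q2W interval to Week 24". Doses fall at Weeks 1, 2, 3, 4, 6 and so on, so dose 5 is Week 6. SAP 4.8.1 plans 4 + 10 = 14 doses. After dose 5 there remain 14 − 5 = 9 doses and 26 − 6 = 20 weeks to the primary assessment. (Protocol 5.5 speaks of three weekly loading doses, which must be reconciled with the four elsewhere. Dose 5 falls long before Week 26 either way.)

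**3. Who has no Week 26 score.** Follow-up runs to 12 weeks after the last dose (Protocol Table 2). SAP 4.1.4 maps follow-up visits to analysis weeks for efficacy and does not window unscheduled data into planned visits.

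| Last dose (week) | Last scheduled follow-up (week) | Scheduled Week 26 EASI |
|---|---|---|
| 6 | 6 + 12 = 18 | no |
| 8 | 20 | no |
| 10 | 22 | no |
| 12 | 24 | no |
| 14 | 26 | yes |

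A patient last dosed at Weeks 6 to 12 completed dose 5, is not replaced, and has no scheduled Week 26 EASI even if every visit is kept. Patients who leave the study or miss the visit are also absent.

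**4. Width by number scored.** The one-sided column uses the formula in step 1. The two-sided column uses the 2.5th percentile of the same Beta distribution and gives the maximum distance from estimate to lower limit.

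| Scored at Week 26 | One-sided exact | Two-sided exact, distance to limit |
|---|---|---|
| 24 | 18.8% | 22.0% |
| 20 | 20.8% | 24.3% |
| 19 | 21.4% | 25.0% |
| 18 | 22.1% | 25.7% |
| 17 | 22.8% | 26.5% |
| 16 | 23.6% | 27.4% |

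From 20 patients, one missing score gives 21.4%, still 21% as rounded; two give 22%. From 24, the count must fall to 18, so 24 − 18 = 6 must be missing.

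**5. How likely that is.** The documents give no loss rate. Assume each patient independently lacks a Week 26 EASI with probability d. The chance of exceeding 21% as rounded is P(X ≤ 18), with X ~ Binomial(N, 1 − d). For N = 20 and d = 0.05 this is 1 − 0.95^20 − 20 × 0.05 × 0.95^19 = 1 − 0.3585 − 0.3774 = 0.264.

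| Assumed loss d | From 20 | From 24 |
|---|---|---|
| 5% | 26% | 0.1% |
| 10% | 61% | 3% |
| 20% | 93% | 34% |

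**The case against.** The strongest reply is that nothing in SAP 2.3 is miscalculated. The statements are conditional on 20 and 24 patients, and they reproduce. That stands: this is a missing allowance for loss, and a reader should not infer an arithmetic error.

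A reader might also infer that losing any one patient breaks the 21%. It does not, because 19 scored gives 21.4%. Nor is the chance that fewer than 20 are scored (64, 88 and 99% from 20 patients at 5, 10 and 20% loss) the chance of exceeding 21%. The latter is the lower set in step 5.

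Stopping treatment is not the same as having no Week 26 score. Under SAP 4.1.4 a patient last dosed at Week 14 or later can still contribute one, and Protocol 7.11 asks for further follow-up assessments after treatment withdrawal. The LOCF analysis would also carry patients with a missing score at the larger n, although it is not the primary analysis.

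The link between evaluable and dose 5 is an inference from one synopsis sentence. Evaluable could mean evaluable for the primary endpoint, in which case 20 would be the right n. That reading is open, but Protocol 7.3 then gives no means of reaching 20, because no one is replaced after dose 5.

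Finally, the interval mismatch matters more. With no loss at all, the two-sided exact interval named in SAP 4.7.1 reaches 24.3% from the estimate at n = 20, already beyond the one-sided 23.6% at n = 16. This is correct, and it means that restating one-sided widths alone would not describe the interval to be reported.

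**Conclusion.** The point holds as a minor one. The plan's own rules do not secure 20 patients scored at Week 26, so the 21% is not a guaranteed ceiling. The shortfall is small: from 20 patients, two missing scores add 22.07 − 20.80 = 1.3 percentage points and four add 23.58 − 20.80 = 2.8. If enrolment reaches 24, the 21% survives up to five missing scores.

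This rests on reading the evaluable count as settled at dose 5 and on loss meaning no Week 26 EASI. The probabilities also rest on assumed, independent losses of 5 to 20%. SAP 4.1.1 plans no hypothesis test and no decision threshold uses the 21%, so the documents do not support a claim that the trial is too small or that a conclusion would change.

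**What to change.** In Protocol 11.1, its synopsis copy and SAP 2.3:

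- Give the precision by number of patients with a Week 26 EASI, for the interval that will be reported. If one-sided exact: 18.8% at 24, 20.8% at 20, 22.1% at 18, 23.6% at 16. If two-sided exact, as maximum distance from estimate to lower limit: 22.0%, 24.3%, 25.7%, 27.4%. Protocol 11.2 and SAP 4.7.1 should name the same interval.
- Say what evaluable means.
- Do not present 20 as the guaranteed minimum n for this interval.

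No extra patients and no change to conduct are needed. The cost is a slightly less favourable stated precision and a small document update. The Protocol part would go through the amendment and IRB approval described in Protocol 12.1 and 12.5, so it could sensibly wait for the next amendment while the SAP is corrected now.
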